### 5.1.2 Exclusion Criteria

An individual who meets any of the following criteria will be excluded from participation in this study:

1. Current suicidal ideation with a plan and/or intent or a suicide attempt within the past 12 months
2. Previous Woebot use
3. Involuntary inpatient psychiatric hospitalization any time within the past 30 days
4. Lifetime diagnosis of bipolar disorder
5. Lifetime diagnosis of a psychotic disorder

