### 8.3.1 Time Frame

Collection of AEs and SAEs will begin at ICF signature, and will continue through EOS at Week 4. Identification of any collected AEs/SAEs from transcript or LDP reviews is anticipated to be completed no earlier than 1 month following the last patient visit and no longer than 4 months from the last patient visit or until all data has been monitored and query cleaned.

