### 8.3.3 AE Outcomes

The Investigator should document the outcome of AE and SAEs as:

- **Resolved**
- **Resolved with sequelae / chronic condition, no resolution expected**
- **Ongoing**
- **Death**
- **Ongoing at time of death**
- **Unknown**

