## 8.5 Safety Monitoring

### 8.5.1 Safety Procedures At Screening

At screening, study participants will be asked to self-report on recent suicidal thoughts including current suicidal ideation with plan and/or intent as well as attempts in the past 12 months. Responses are not monitored in real time. Participants who endorse having a current suicidal plan or intent or an attempt in the past 12 months will be excluded from the study. Participants will be notified that:

- They may benefit from a level of care beyond the scope of the study and investigational treatment.
- They should call 9-1-1 or go to their local emergency room and reach out to someone they trust and can help them stay safe if they feel they are in crisis or in need of medical attention.
- Will be electronically provided with a list of resources.

Participants who endorse **current** suicidal ideation with a plan **or** intent will also be notified that a member of the study team will attempt to follow-up with them. Three attempts will be made by the Study PI to contact participants by phone and/or email. The study team will make every effort to follow-up with the participant as soon as possible and no more than 3 business days following the initial report.

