#### **8.5.3 Safety Event Solicited Self-Report Survey**

[figure not shown]
Study participants will be asked to self-report on potential safety events at the Week 2 and Week 4 timepoints. Questions will explicitly ask about changes in the past two weeks to their (1)medication and/or therapy, (2) mental and/or physical health, and (3) any new thoughts about ending their life including new intent/plan/or attempts. Information gathered through this survey will be used to inform the need for follow-up, AEs/SAEs/UAPs/UADEs/Device Deficiencies/UADE determination, and resolution.

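### As described, the Week 2 and Week 4 safety survey has no status question for earlier events and asks only about new suicidal thoughts, so it cannot by itself separate resolved from ongoing ideation

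*Combined protocol and SAP*

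**What the plan says.** Section 8.5.3 gives the survey three topics. The first two are described thus: "Questions will explicitly ask about changes in the past two weeks to their (1)medication and/or therapy, (2) mental and/or physical health". The third is "any new thoughts about ending their life including new intent/plan/or attempts". The same paragraph sets out the purpose: "Information gathered through this survey will be used to inform the need for follow-up, AEs/SAEs/UAPs/UADEs/Device Deficiencies/UADE determination, and resolution".

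Four other places bear on this:

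- **8.3.3 AE Outcomes:** "The Investigator should document the outcome of AE and SAEs as" one of six categories, with Resolved and Ongoing among them.
- **5.1.2 Exclusion Criteria:** the suicidality exclusion is "Current suicidal ideation with a plan and/or intent or a suicide attempt within the past 12 months". Ideation without plan or intent does not exclude.
- **8.5.1 Safety Procedures At Screening:** participants are asked to "self-report on recent suicidal thoughts including current suicidal ideation with plan and/or intent", so a screening answer exists to compare with.
- **8.3.1 Time Frame:** "Collection of AEs and SAEs will begin at ICF signature, and will continue through EOS at Week 4".

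Table 1 places the survey at Day 14 (+6) and Day 28 (+6), with no later administration.

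**The concern.** The stated purpose and the described content do not fully match. Resolution is a question about current status, whereas the suicidality item is about onset. A participant who reported suicidal thoughts at Week 2 and still has them unchanged at Week 4 can truthfully report nothing new, and so can one whose thoughts have gone. The participant is also left to judge what counts as new, and 8.5.3 does not say whether the reference is screening, the previous survey or the two-week window.

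The people most affected are those who enter with ideation but no plan or intent. For them, continuing thoughts are not new, and more frequent or intense thoughts are not specifically asked about. At stake is whether a persisting or worsening problem comes to the study team's attention in time, and whether the outcome recorded under 8.3.3 rests on evidence.

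**Working it through.** The plan gives no event rate or other figure to reproduce here. The check sets the described items against the situations they must distinguish, taking the two-week recall to apply to all three topics.

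**Step 1: truthful answers at Week 4.**

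| Situation | Item (3), new thoughts, intent, plan or attempt | Item (2), change in health | Status under 8.3.3 |
|---|---|---|---|
| Thoughts reported at Week 2, since gone | No | Yes, if recovery is counted as a change | Resolved |
| Thoughts reported at Week 2, unchanged | No | No | Ongoing |
| Thoughts present at entry, unchanged | No | No | Not clearly an AE (8.2.1) |
| Thoughts present at entry, more frequent or intense, no plan or intent | No, read literally | Yes, if counted as a change | For the investigator to judge |
| Escalation to plan, intent or attempt | Yes | Possibly | Elicited |

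On item (3) the first two rows are identical although their status differs. They separate only if the recovered participant volunteers recovery under item (2), which is not described as naming suicidal thoughts. The fourth row also depends on item (2). The third is elicited by no described item.

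**Step 2: survey timing.** The surveys fall on Day 14 to 20 and Day 28 to 34.

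- Shortest interval: 28 − 20 = 8 days. With 14-day recall, 14 − 8 = 6 days are covered twice.
- Longest interval: 34 − 14 = 20 days. Then 20 − 14 = 6 days are covered by neither survey.

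An event first reported at Week 4 has no later survey to show its course.

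**Step 3: other routes.** Section 8.3 lists three AE sources: spontaneous reports, this survey, and review of selected transcripts.

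- Spontaneous reports depend on the participant volunteering.
- Transcript review is selective. Section 8.3.1 expects identification from transcripts and the Language Detection Protocol (LDP) to finish between 1 and 4 months after the last patient visit, or when data are monitored and cleaned. It is not described as a timely trigger.
- The LDP (8.5.4), in its visible text, reminds participants of the app's limits and offers resources. No staff alert is described.
- Unscheduled visits (8.5.2) require participant contact or the team learning of an event, and the survey is one of the ways it would learn.
- Section 8.4 has follow-up information updated as it is collected, but sets no status check.

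The survey is thus the only solicited safety source visible after screening, and none of the other routes clearly supplies the missing status information.

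**The case against.** Much of the case on the other side stands.

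- **A reader might infer that the survey cannot show resolution at all.** The text does not support that. Items (1) and (2) give no direction of change, so recovery can be reported. The survey need only inform resolution; the investigator records the outcome, can choose Ongoing or Unknown, and has follow-up under 8.4 and 8.5.2. A participant who reported suicidal thoughts at Week 2 may already be in direct contact with staff.
- **A reader might infer that worsening is missed altogether.** It is not. New intent, plan or attempts are asked about explicitly, and other worsening can be reported as a change in mental health. The gap is intensification short of plan or intent.
- **A reader might infer that AE counts will look too favourable.** Sections 10.3.1 and 10.3.2 report event frequency as n(%), so a Week 2 event stays counted whatever the Week 4 answer. No passage says a negative answer is read as resolution, and unchanged baseline ideation is not clearly an AE under 8.2.1.
- **A reader might put an error rate on it.** Assume 20 of 200 participants report an event at Week 2 and 25% to 75% persist unchanged. Then 20 × 0.25 = 5 to 20 × 0.75 = 15 would answer nothing new while ongoing. Both inputs are invented, and the resulting error simply equals the assumed persistence.

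The evidence is also incomplete. Section 8.5.3 is a summary; the item wording is not provided, a figure there is not shown, Table 1 has redacted rows, and the Safety Management Plan is not available. Asking about onset is a defensible way to find new AEs. What it does not do is supply the status information that 8.5.3 says the survey will help provide.

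**Conclusion.** The point holds in a limited form. As 8.5.3 describes it, the survey has no explicit status question for earlier events and no explicit question on ideation that persists or intensifies without plan or intent, although such ideation is eligible at entry. A Week 4 report of nothing new cannot on its own distinguish Resolved from Ongoing for suicidal thoughts.

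This is a weakness in monitoring and outcome ascertainment that is cheap to mend. The documents do not show a biased AE count, and they give no basis for sizing the problem. The conclusion assumes that the survey's items match their description in 8.5.3 and that neither the redacted assessments nor the Safety Management Plan already collects this information.

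**What to change.** Make three changes to the survey and its description:

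1. Reword item (3) to ask about any thoughts of ending life, intent, plan or attempt within the recall period. Staff, not the participant, then classify the answer as new, worsened or unchanged against the screening answer from 8.5.1.
2. Add one Week 4 status question for each event reported at Week 2: resolved, improved, unchanged or worse.
3. State in 8.3.3 AE Outcomes that the outcome comes from that answer or from direct follow-up, never from the absence of a new report.

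If the survey in use already contains such items, correct 8.5.3 to match it.

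The cost is an IRB-approved wording amendment and a branching question in the existing electronic survey, with no extra visit. There will be more positive answers to review, including from participants with stable baseline ideation, and some may lead to contact under 8.5.2. How those answers are handled stays with the Safety Management Plan; no clinical rule is proposed here.

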#### **8.5.4 Language Detection Protocol (LDP)**

In addition to the onboarding screens re-stating that Woebot is not a crisis service, DISC-MA has a Language Detection Protocol (LDP), developed by Woebot Health. The purpose of the LDP is to detect potentially concerning topics within participant-input free-text and will be enacted for all participants in the study. Upon detection of any concerning topics, LDP initiates a conversation to remind the participant of the application's limitations of services and offer a resource list which includes readily accessible support channels. If a possible mention of concerning topics is detected, the participant is reminded of the limitations of services (which they will have already seen in both the informed consent and well as Woebot's onboarding screens) as well as offered a list of external-to-application resources, specifically contact information, that have been curated in consultation with suicide prevention experts. This resource list includes emergency contact phone numbers, and suicide ideation and domestic violence hotline information.

## 8.6 Safety Assessment Committee (SAC)

The SAC is the formal WH committee charged with responsibility for the review and evaluation of previous as well as accumulating data from clinical studies of WH devices, to assess safety, perform signal confirmation and risk assessment, assess the risk-benefit associated with study continuation, efficacy and other trial conduct issues such as scientific merit, and to develop recommendations so as to ensure safety across studies and minimize risk for subjects. The SAC members will include the following individuals:

1. Independent Medical Safety Expert, who will serve as the SAC Chair;
2. A Clinical Development Lead;
3. a Medical Lead;
4. a Regulatory Lead;
5. a Device Vigilance Lead

Validated, accurate and interpretable data are to be provided to the SAC, as requested. Data files to be used for SAC analyses will undergo established data review/QC procedures to the extent possible and critical fields will be identified. The Sponsor must ensure that data is of sufficient quality to support the performance of safety surveillance and confirm the assessment of causality associated with the event(s), the associated WH application and confirmation of reportability.

The SAC will determine whether any missing data will significantly impact the safety assessment and will direct the necessary actions to address missing data.

## 8.7 Quality Control and Quality Assurance

The Sponsor maintains a robust Quality Management System (QMS) that includes all activities involved in quality assurance and quality control per 21 CFR 820, to ensure compliance with written SOPs as well as applicable global/local GCP regulations and ICH Guidelines.

Audits of investigator sites, vendors, and Sponsor systems are performed by auditors, independent from those involved in conducting, monitoring, or performing quality control of the clinical trial. The clinical audit process uses a knowledge/risk-based approach.

Audits are conducted to assess 21 CFR 820 and GCP compliance with global and local regulatory requirements, protocols and internal SOPs and are performed according to specified Sponsor processes.

## 9. Statistical Analysis

### 9.1 General Methodology

Given the exploratory nature of this study, and its hypothesis-generating purpose, analyses will be descriptive in nature and will not include significance testing. Descriptive statistics for all endpoints will be reported for the full sample. All continuous variables will be tested for normality using a skewness cutoff of 1.00. For continuous variables, means and standard deviations will be reported if the data are normally distributed; for non-normal data, medians and interquartile ranges will be reported.

Frequencies and percentages will be reported for categorical variables. The amount of missing data will be summarized. Where applicable, bivariate comparisons will be conducted using chi-squared tests, Fisher exact test, t-tests, one-way ANOVA, Person's correlation, and Spearman's correlation. However, no hypothesis testing will be completed, and only effect sizes and 95% confidence intervals will be provided where applicable. For departures from normality, the appropriate non-parametric method will be applied.

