Statistical Methods:	
Descriptive statistics will be reported for study measures. Summary reports will be presented for all time periods independently. [REDACTED]
 
[REDACTED]
 
[REDACTED]
 
[REDACTED]
 
Bivariate analyses will use chi-squared tests, Fisher exact test, t-tests, one-way ANOVA, Person's correlation, and Spearman's correlation, where applicable. No hypothesis testing will be completed, and only effect sizes and 95% confidence intervals will be provided where applicable. For departures from normality, the appropriate non-parametric method will be applied.

Protocol Version and Date:	1.1 (18 /MAR /2024 )
Keywords:	digital mental health intervention, chatbot, conversational agent, relational agent, natural language processing, artificial intelligence

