### 9.2 Analysis Sets

Primary analyses will be completed on two sets of data - the full intent-to-treat (ITT) sample of anyone randomized with available survey data, as well as a per-protocol (PP) sample (i.e., registered for app, completed all assessment timepoints, no protocol deviations, etc).

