#### 10.1.3 Endpoints

Therapeutic alliance will be measured by the Working Alliance Inventory (WAI) total scale score at week 1 and WAI total scale score at week 4.

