#### 10.1.4 Analysis Plan

Descriptive statistics will be used to describe therapeutic alliance at week 1 and week 4 of the intervention. Descriptive statistics will also summarize socio-demographic characteristics of the sample.

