## 10.4 Demographic and Baseline Characteristics

Demographic and baseline characteristics will be summarized for the full sample. Continuous variables will be summarized using tables of descriptive statistics, with normally distributed variables summarized by mean and standard deviation and non-normal data summarized by median and interquartile range (IQR). Categorical and ordinal variables will be described using frequencies and percentages.

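### The skewness rule in section 9.1 can put WAI total at week 1 and at week 4 on different summary statistics, so the two primary results may not be directly comparable (low severity)

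*Combined protocol and SAP*

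**What the plan says.** Section 9.1 sets the rule: "All continuous variables will be tested for normality using a skewness cutoff of 1.00". It continues: "means and standard deviations will be reported if the data are normally distributed; for non-normal data, medians and interquartile ranges will be reported". This is one summary or the other, not both. Section 10.4 uses the same split for demographic and baseline data.

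Section 10.1.3 defines the primary endpoint as two scores: "Therapeutic alliance will be measured by the Working Alliance Inventory (WAI) total scale score at week 1 and WAI total scale score at week 4". Section 10.1.4 fixes no particular statistic for them: "Descriptive statistics will be used to describe therapeutic alliance at week 1 and week 4 of the intervention". The Protocol Synopsis adds: "Summary reports will be presented for all time periods independently".

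Section 9.2 says: "Primary analyses will be completed on two sets of data", namely ITT and per-protocol. Section 10.5 rules out imputation, so the number of observations can differ between weeks. Section 9.3 targets N=200 without a formal calculation.

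**The concern.** In this study the descriptive summary is the whole primary result: there is one arm, no test and no sample-size calculation. Section 10.1.2 expects alliance at the beginning and end of treatment to generate hypotheses, so readers will naturally set the two weeks side by side.

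Read as written, section 9.1 treats each week's WAI total as a variable of its own and chooses its statistic from its own sample skewness, which is a noisy quantity. If the true skewness is near 1.00, chance alone can send one week to mean (SD) and the other to median (IQR). For a skewed score these measure different things, and the gap between them would sit on top of any real difference between the weeks.

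**Working it through.** The plan states no figure to reproduce. The check asks how often the rule would split the two weeks, and how far apart the two statistics then are.

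**Inputs from the documents.** Cutoff 1.00 (9.1); two WAI totals (10.1.3); N=200 (9.3); no imputation (10.5).

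**Assumptions, because the documents are silent.**
- The rule acts on absolute skewness; section 9.1 gives no sign convention.
- The check is made separately at each week.
- True skewness is the same at both weeks and ranges from 0.5 to 1.0.
- Within-person correlation is 0.6 (Gaussian copula).
- Scores are left-skewed, with either a gamma shape (unbounded) or a beta shape (bounded, second parameter 1 to 2). A 12-item total has a floor and a ceiling, so the beta shapes are the more natural model.

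**Step 1: noise in sample skewness.** Under normality SE = sqrt[6n(n−1) / ((n−2)(n+1)(n+3))]. At n=200 this is sqrt[6×200×199 / (198×201×203)] = sqrt(238,800 / 8,078,994) = 0.172. It is 0.192 at n=160 and 0.221 at n=120. A true skewness of 0.8 is therefore little more than one standard error from the cutoff.

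**Step 2: chance that the two weeks receive different statistics.** Simulation, n=200 at both weeks:

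| True skewness | Bounded (beta) | Gamma |
|---|---|---|
| 0.5 | about 0% | 2-3% |
| 0.7 | 2-5% | about 13% |
| 0.8 | 11-17% | 23-24% |
| 1.0 | 42-45% | 42-44% |

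With n=140 at week 4, the gamma results are 3% at 0.5, 25% at 0.8 and 43% at 1.0, so attrition changes little.

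**Step 3: distance between mean and median at skewness 1.0.**
- Gamma: shape k = 4/skewness² = 4, so mean 4, SD 2 and median 3.672. Gap = (4 − 3.672)/2 = 0.164 SD.
- Beta with second parameter 1: skewness = 2(1−a)·sqrt(a+2) / ((a+3)·sqrt(a)), which is −1.0 at a = 3.70. Mean = 3.70/4.70 = 0.787; median = 0.5^(1/3.70) = 0.829; SD = sqrt[3.70/(4.70²×5.70)] = 0.171. Gap = 0.042/0.171, about 0.25 SD. With second parameter 2 it is 0.19 SD.

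**Step 4: comparison with sampling precision.** The 95% CI half-width of a mean is 1.96/sqrt(n) in SD units: 1.96/sqrt(200) = 0.139 and 1.96/sqrt(140) = 0.166. The gap of 0.16-0.25 SD is larger than the half-width at n=200. At n=140 the gamma gap (0.164) is just below it and the beta gaps (0.19-0.25) are above it.

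**Step 5: after the fix.** If both statistics are always shown, a mismatch cannot occur.

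**The case against.** The strongest reply is that the rule is objective and prespecified, that the study is exploratory, and that no visible text plans a change score, test or decision comparing the two weeks. The Synopsis says that time periods are summarised independently. All of this stands, and it limits the severity.

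A reader might infer more than the documents support:

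- **That a real difference could not be told from a change of statistic.** A table labelled mean (SD) at one week and median (IQR) at the other shows the switch. Direct comparability is lost, but nothing is hidden.
- **That a mismatch is likely.** The figures above 40% come from placing the true skewness on the cutoff. For a bounded score at skewness 0.7 the chance is 2-5%, and at 0.5 it is about zero.
- **That ITT and per-protocol results will also differ in statistic.** Section 9.1 applies the rule to variables and does not say that it is re-run in each set. This is possible, but it is an inference.
- **That the mean-median gap always exceeds the confidence interval half-width.** It does not for the gamma shape at n=140.
- **That letting a symmetric two-peaked distribution through as normal adds to the problem.** Skewness alone is a weak normality check, but in such a distribution the mean and median coincide, so no conflict between them arises.

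Parts of the statistical text are redacted, including text next to the Synopsis sentence on time periods. The absence of a common statistic can be asserted only for the visible text.

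**Conclusion.** The point holds with low severity. The visible plan allows the two primary WAI results to be reported on different statistics and nothing in it prevents this. With absolute skewness as the trigger, n=200 at both weeks, correlation 0.6 and equal true skewness, the chance is about 0-3% at skewness 0.5, 11-24% at 0.8 and 42-45% at 1.0, across bounded beta to gamma shapes. If it happens near the cutoff, the two statistics differ by about 0.16-0.25 SD with no real change in alliance. That is similar to or larger than the half-width of a 95% CI for the mean (0.14 SD at n=200, 0.17 SD at n=140). WAI skewness, the correlation and the sign convention are all assumed. If the true skewness is about 0.5 or less, the issue hardly arises. The harm is to the descriptive reading of alliance over time; no error rate is involved.

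**What to change.** In sections 9.1 and 10.1.4, state that for WAI total at week 1 and at week 4 the report will give n, mean (SD) with 95% CI and median (IQR), whatever the skewness, and in the same format for the ITT and per-protocol sets. Give the skewness value as a descriptor only; for this endpoint it should no longer select the statistic. The rule may stay for other variables, but section 9.1 should then say whether the cutoff applies to the absolute value.

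The cost is one sentence in the plan and two more table columns. No new data are needed and the sample size does not change.
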